## 4.8 Allocation of Patient Numbers

After signing of the Informed Consent/Accent Form (ICF/AF) by patients and/or patients' legal representatives, if applicable, patients will be assigned a unique patient ID number.

A patient ID number will consist of six digits. The first three digits represent the site code (00X for the X site). These three digits will be used in combination with a three-digit rolling number that will be sequentially assigned by the site to patients who sign the ICF/AF. This number would start at 001 for each site. For example, if site 001 has eight patients, the patient ID number would be 001001 to 001008. The patient ID number would start again for site 002 at 002001. If a patient is withdrawn after receiving his or her patient ID number, the number will not be reused. For the purpose of the study, patients will be referred to by their patient ID number.

## 4.9 Method of Assignment to Treatment

At the baseline visit, patients will be randomly assigned to receive deferiprone or deferoxamine in a 2:1 ratio. Stratified randomization based on disease category (sickle cell disease vs. other anemias) and on the transfusional iron input in the 3 months prior to baseline ( $> 0.3$  mg/kg/day vs.  $\leq 0.3$  mg/kg/day) will be employed to ensure that the 2:1 ratio is maintained within each of the 4 strata: 1) sickle cell disease with transfusional iron input  $> 0.3$  mg/kg/day, 2) sickle cell disease with transfusional iron input  $\leq 0.3$  mg/kg/day, 3) other anemias with transfusional iron input  $> 0.3$  mg/kg/day, and 4) other anemias with transfusional iron input  $\leq 0.3$  mg/kg/day. A randomization list will be generated for each stratum, assigning study medication to individual randomization numbers in blocks of 6. Treatment assignment and drug allocation will be performed by an Interactive Voice Response System (IVRS).

# 5 STUDY PROCEDURES

## 5.1 Entry Procedures

An Informed Consent Form (ICF)/assent form (AF) approved by a recognized IRB/IEC, and local regulatory bodies, if applicable, will be signed and dated by the patient and when applicable, the patient's authorized legal representative prior to the patient's participation in this study. The patient and/or legal representative, if applicable, will then

be provided with a copy of the signed ICF/AF. The original ICF/AF will be kept by the Investigator. Patients who sign an ICF/AF will undergo Baseline Phase procedures.

All transfusions must be performed during a study visit (i.e., during weekly, biweekly, monthly, quarterly, or semi-annual visits) for the entire study duration, except for those patients who may require emergency transfusion. Data of all transfusions performed during the trial, including type of transfusion (simple, exchange, partial exchange), volume of blood that the patient received during the transfusion, and the mean hematocrit of the packed red blood cell units transfused, must be recorded in the eCRF and source documents. Iron input per transfusion will be calculated based on the information collected throughout the study.

## 5.2 Screening/Baseline Visit (Day -60 to Day -1: Visit -1)

Assessment of eligibility:

The following procedures will take place at the Screening/Baseline visit:

- Explain the study to the patient and/or parent/legal representative, obtain written informed consent/assent, and give a copy to the patient and/or parent/legal representative;
- Assign the patient ID number (see [Section 4.8](#));
- Review previous/current chelation therapy;
- Record demographic information;
- Obtain medical history;
- Obtain transfusion history;
- Record prior and current medication(s);
- Collect blood sample for hematology, biochemistry (fasting glucose; patient must come to the site following a 10-hour fast), and serology (to be conducted within 14 days of starting study medication; will be considered as the baseline procedures for biochemistry);
- Collect blood sample for pregnancy testing for all females of childbearing potential. A negative result will be required for start of dosing;
- Collect urine for urinalysis;
- Perform physical examination (to be completed by Investigator or a qualified delegate);
- Take vital signs, weight, and height;
- Perform 12-lead ECG;
- If patient is identified as potentially eligible based on the available data (medical history, transfusional history, current medication(s), physical examination, vital signs), perform MRI scan for:

- Liver, and transmit to a central laboratory for interpretation and LIC calculation (to be conducted within two months prior to starting study drug; will be considered as the baseline procedure);
- Cardiac MRI T2\*, and transmit to a central laboratory for interpretation (to be conducted within two months prior to starting study drug; will be considered as the baseline procedure);
- Conduct contraceptive counselling for all sexually active patients;
- Review inclusion/exclusion criteria;
- Remind the patient, and/or if applicable patient's authorized legal representative, that she/he must carefully keep track of medical events and medication used to treat them;
- Instruct eligible patients to start washout of current chelation therapy (if required) 7 days prior to the baseline visit, and washout of hydroxyurea (if required) 30 days prior to the baseline visit;
- Schedule next study visit.

### 5.3 Baseline Visit (Day 0, Visit 0)

#### Enrolment and Baseline Assessments:

Once the results of the screening/baseline visit procedures have been obtained, they should be reviewed against the inclusion/exclusion criteria to confirm the patient's eligibility to enter the trial. If the patient is determined to be eligible, perform the following Baseline assessments:

- Collect blood sample for hematology (the results of this procedure will be considered the baseline values). An ANC value of  $>1.5 \times 10^9/L$  will be required for start of dosing;
- Collect blood sample for serum ferritin;
- Collect blood and urine samples for pregnancy testing for all females of childbearing potential. A negative result of the urine test will be required for start of dosing. This result will have to be reconfirmed by the results of the serum pregnancy test;
- Determine if patient has had any medical events or used any new medications/changed medications or changed dose or frequency of medication since the screening visit. If so, document them as specified in [Sections 8.2.1](#) and [8.2.4.3](#);
- Confirm eligibility;
- Randomize patient;
- Take vital signs (including weight);

- Collect blood sample for assessing genetic polymorphism related to deferiprone - induced agranulocytosis (optional);
- Complete patient-reported quality of life questionnaire (SF-36 or Child Health Questionnaire);
- Review and update transfusion history;
- Conduct contraceptive counselling for all sexually active patients;
- Perform dose calculation;
- Dispense study medication as per [Section 7.4](#);
- Instruct the patient, and/or if applicable patient's authorized legal representative, how to take the medication;
- Remind the patient, and/or if applicable patient's authorized legal representative, that all used (empty bottles) and unused medication must be returned at each monthly study visit;
- Provide a patient diary card, explain how to complete it, and remind patient to return completed card at next visit;
- Remind patient to visit the site or a local laboratory for the weekly blood draws;
- Remind the patient, and/or if applicable patient's authorized legal representative, that she/he must carefully keep track of adverse events and medication used to treat them;
- Remind the patient, and/or if applicable patient's authorized legal representative, that if study medication is stopped early, she/he must return to the clinic for an Early Termination Visit as soon as possible, but no later than 1 month following study medication discontinuation;
- Remind patient, and/or if applicable patient's authorized legal representative, that if an infection develops, therapy must be interrupted immediately. Patients should be advised to report immediately to their physician any symptoms indicative of infection such as fever, sore throat, and flu-like symptoms. In presence of confirmed fever and/or infection, they will be required to have their neutrophil counts tested as soon as possible and no later than 24 hours after the symptoms of infection are detected;
- Provide patient and/or if applicable patient's authorized legal representative with an emergency card and advise her/him to carry this card at all times;
- Schedule next study visit.

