### **3 INVESTIGATIONAL PLAN**

#### **3.1 Overall Study Design**

This study is a 52-week, prospective, multi-center, two-arm, randomized, open-label, parallel design of deferiprone therapy vs. deferoxamine. The study will consist of a Baseline Phase and a Treatment Phase. Three hundred (300) male and female patients with sickle cell disease (SCD) or other anemias requiring blood transfusion will be enrolled.

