##### **Deferiprone treatment arm:**

During the study, patients will be prescribed Ferriprox 500 mg tablets or deferiprone 80 mg/mL oral solution, according to patient preference or product's availability, for administration three times a day (tid). The dose of deferiprone will be based on the transfusional iron input and the severity of iron load at baseline, and may be adjusted on the basis of the magnitude of change in iron overload during the study.

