### **3.3 Study Sites and Study Duration**

Study sites will be located in but not limited to countries in North America, Europe, and the Middle East. While the goal will be to keep the number of sites to a minimum, it is expected that the study will engage sites worldwide due to the anticipated difficulty in enrolling patients with a 33% probability of being allocated to the deferoxamine treatment arm.

Each patient is expected to participate in the study for approximately 60 weeks (from the Screening Visit to the End of Study Visit).

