### **11.2.2 Secondary Efficacy Endpoints**

- Change from baseline to Week 52 in patient-reported quality of life (SF-36 or Child Health Questionnaire);
- Change from baseline to Week 52 in cardiac MRI T2\*;
- Change from baseline to Week 52 in serum ferritin.

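### Protocol 5.3 lists the baseline quality-of-life questionnaire after randomisation at an open-label visit, and nothing requires it before the arm is known, so the change from baseline may be biased

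*Protocol*

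**What the plan says.** Protocol 4.9 puts randomisation at the Day 0 visit: "At the baseline visit, patients will be randomly assigned to receive deferiprone or deferoxamine in a 2:1 ratio". Protocol 5.3 then lists that visit's procedures. Eligibility is confirmed, followed by "Randomize patient", vital signs, an optional genetic sample, and then "Complete patient-reported quality of life questionnaire (SF-36 or Child Health Questionnaire". Dose calculation and dispensing come later in the list.

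Protocol 3.1 describes the trial as "randomized, open-label, parallel design of deferiprone therapy vs. deferoxamine". In one arm, "patients will be prescribed Ferriprox 500 mg tablets or deferiprone 80 mg/mL oral solution" (Protocol 3.2). The other arm receives subcutaneous infusions of 8 to 12 hours on five to seven days a week.

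Protocol 11.2.2 lists as a secondary efficacy endpoint "Change from baseline to Week 52 in patient-reported quality of life (SF-36 or Child Health Questionnaire". Adults complete the SF-36. For patients aged 17 and under, the parent and child forms of the CHQ are both used where possible (Protocol 8.1.2.1). SAP 7.2 refers the analysis of these instruments to a separate SAP, which is not among the documents.

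**The concern.** A baseline should be measured before allocation can influence it. Here the score is a rating by the patient or parent. As listed, it is collected after the patient has been assigned either an oral drug or long infusions on most days of the week. The sponsor expected the comparator to be unpopular: Protocol 3.3 cites "anticipated difficulty in enrolling patients with a 33% probability of being allocated to the deferoxamine treatment arm". A reaction to the allocation is therefore plausible, although that sentence concerns recruitment and not questionnaire answers.

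The other efficacy baselines are better protected. The liver and cardiac scans are done at screening and read centrally, and the ferritin sample is listed before randomisation. Quality of life is the only efficacy measure with a subjective baseline, and the only one whose baseline is listed after allocation. At stake is the comparison that serves the quality-of-life objective in Protocol 2.2. If patients assigned to infusions rate themselves lower on Day 0, their change score rises by the same amount, and deferoxamine appears to improve quality of life more than it did.

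**Working it through.** The plan gives no quality-of-life effect, standard deviation (SD), power or sample size, so it has no figure to reproduce. The check compares the passages on timing and then works out how a shift would carry through.

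**1. Does any passage fix the order?**
- Protocol 5.3: randomisation is the sixth bullet and the questionnaire the ninth.
- Protocol 8.1.2.1: the questionnaires are due at baseline, Week 26 and Week 52. Nothing is said about before or after randomisation.
- Protocol Appendix 18.1 and SAP Table 1: both procedures stand in the same Baseline column, with no footnote on sequence.
- SAP 7.2: the endpoint is named and its analysis deferred to the separate SAP.

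No passage requires completion before allocation is known. None says that the bullets must be done in the order printed.

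**2. How would a shift carry through?** Suppose there is no true effect and knowing the arm lowers the Day 0 score in the deferoxamine arm by d. Let the slope of the Week 52 score on the true baseline be ρ. For deferiprone minus deferoxamine:
- change score, unadjusted: bias = −d
- change score adjusted for the Day 0 score: bias = −ρd
- Week 52 score alone: no bias from this source

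A simulation with assumed inputs (d = 0.2 SD, unit variances, 200 versus 100 patients) gives the following. It is an illustration only.

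| ρ (assumed) | Unadjusted bias (SD) | Adjusted bias (SD) |
|---|---|---|
| 0.4 | −0.20 | −0.08 |
| 0.6 | −0.20 | −0.12 |
| 0.8 | −0.20 | −0.16 |

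Adjustment shrinks the bias but does not remove it. With d = 0 there is none. I give no false-positive rates. They depend on the group sizes per instrument and on an alpha for quality of life, and the documents state neither. The 0.0399 level is specified for LIC, cardiac T2* and ferritin only.

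**3. Could the enrolled patients' data show a shift?** Scores taken before allocation should differ between arms only by chance, so the Day 0 difference estimates d. Suppose all 213 patients in the SAP's interim projection (142 and 71) used one instrument. The standard error would be √(1/142 + 1/71) = √0.0211 = 0.145 SD, and the 95% half-width 1.96 × 0.145 = 0.28 SD. The real groups are split by instrument, so their intervals will be wider. The check can reveal a large shift but cannot exclude one of 0.2 SD.

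**4. How much of the SF-36 can react?** In Appendix 18.5, items 4 to 10 ask about the past four weeks. They contain 4 + 3 + 1 + 1 + 1 + 9 + 1 = 20 of the 36 questions. The other 16 cover general health, comparison with a year ago, current limitations and health beliefs. The CHQ content printed in the same appendix shows no four-week recall wording.

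**The case against.** The strongest reply is that the list in 5.3 is a checklist and not a timed sequence. Two items support this. Weight and the transfusion-history update both follow randomisation in the list, yet both bear on the iron-input stratum. The SAP 9.3 example divides by baseline body weight. This stands as a caution. It does not settle the matter, because weight and transfusion history were already taken at screening, and the main steps (samples, eligibility, randomisation, dosing, dispensing) do follow working order. If the order is free, sites may differ and the baseline is still unprotected.

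The four-week recall also counts. News received minutes earlier cannot alter the period being rated. It can act only through mood or expectation, more plausibly on the general-health questions. That limits the likely shift on the SF-36 without excluding one.

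The separate quality-of-life SAP may already handle the baseline suitably. The Week 52 ratings are open-label as well, so a clean baseline would not make the endpoint blind. And the direction described above would work against the sponsor's drug. All three points are fair, and they lower the importance of the issue.

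A reader might infer that every patient answered knowing the arm and that the endpoint is therefore biased, with a badly inflated error rate. The documents do not support this. They give no completion times, no evidence of a differential shift and no variance. Any error rate computed for 142 against 71 patients on one scale matches no analysis that can be run, because adults and children use different instruments.

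**Conclusion.** The point holds as a risk of bias of unknown size in one secondary endpoint. As written, the plan allows a self-reported or parent-reported baseline to be collected after allocation in an open-label trial, and nothing in the protocol or SAP prevents it. Whether bias arises depends on two things the documents do not show: that sites followed the printed order, and that knowing the arm moved Day 0 answers differently in the two arms. The primary endpoint is not affected. This is a cheap improvement and does not threaten the trial's main conclusion.

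**What to change.** **If enrolment restarts.** In Protocol 5.3, move the questionnaire above the randomisation step. State that it must be completed before the allocation call and before the patient or parent is told the arm. This needs a short signed amendment under Protocol 14.6, with ethics approval if it is judged to affect scientific quality, but no extra visit or test. According to the SAP, enrolment is on hold and the decision to restart rests on DSMB advice, so this part helps only future patients.

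**For patients already enrolled.** Do the following separately for SF-36 and CHQ, unless the quality-of-life SAP already provides it:
- Compare Day 0 scores between arms with confidence intervals. Do not read a non-significant difference as proof of no shift.
- Where completion times were recorded, report whether the questionnaire preceded allocation.
- Add a sensitivity comparison of Week 52 scores that does not use the Day 0 score.

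The sensitivity analysis costs precision. With equal variances, its standard error is 1/√(1 − ρ²) times that of the baseline-adjusted analysis: 1.09, 1.25 and 1.67 for ρ = 0.4, 0.6 and 0.8. It should therefore stand beside the planned analysis and not replace it.

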## 5.4 Weekly or Biweekly Assessments

The hematology assessments that are required weekly ( $\pm$  3 days) up to Week 26 and biweekly ( $\pm$  3 days) thereafter can be conducted at local laboratories or study sites, and will consist of the following procedures:

- Collect blood sample for hematology. Hematology results should be reviewed by the Investigator as soon as they are received from the laboratory;
- If a patient is receiving a blood transfusion during this visit or has received blood transfusions since the last visit (except for those patients who received an emergency transfusion), record the type of transfusion (simple, exchange, partial exchange), volume of blood that the patient received during the transfusions, and the mean hematocrit of the packed red blood cell units transfused (data obtained from the site's blood bank).

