## 5.9 End of Study Visit (Week 52 or Early Termination Visit)

The End of Study assessment (at 52 weeks  $\pm$  7 days from the start of study medication) or Early Termination will consist of the following procedures:

- Perform physical examination;
- Review medical history and concurrent medications;
- Take vital signs, weight, and height;
- Collect blood sample for serum ferritin, hematology, biochemistry (fasting glucose; patient must come to the site following a 10-hour fast), and serology;
- Collect blood sample for pregnancy testing for all females of childbearing potential;
- Collect urine for urinalysis;
- Perform 12-lead ECG;
- Perform MRI scan for:
  - Liver, and transmit to a central laboratory for interpretation and LIC calculation;
  - Cardiac MRI T2\* and transmit to a central laboratory for interpretation;
- Complete patient-reported quality of life questionnaire (SF-36 or Child Health Questionnaire);
- Review patient diary card with the patient, and/or if applicable patient's authorized legal representative, then collect and file the diary card with the source documents;
- Determine if patient has had any AEs or SAEs or used any concomitant medications. If so, document them as specified in [Sections 6.3](#) and [8.2.4](#);
- If the patient has received blood transfusions since the last visit (except for those patients who received an emergency transfusion), record the type of transfusion (simple, exchange, partial exchange), volume of blood that the patient received during the transfusions, and the mean hematocrit of the packed red blood cell units transfused (data obtained from the site's blood bank);
- Collect and account for the medication dispensed at the previous applicable visit;
- Explain to the patient, and/or if applicable the patient's authorized legal representative, that she or he should inform the site if she/he experiences any serious medical problems (SAEs) in the 30 days following the last dose;
- Follow up on any continuing adverse events or serious adverse events until resolution, until the condition stabilizes, until the event is otherwise explained, or until the patient is lost to follow-up.

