## CLINICAL STUDY PROTOCOL

STUDY CODE: LA38-0411

STUDY PROCEDURE	Baseline Phase				Treatment Phase			
	Screening/ Baseline	Baseline	Hematology Assessments 	Telephone Calls (Week 1, 2, 3)	Monthly Visits (Week 4, 8, 16, 20, 32, 36, 44, 48)	Quarterly Visits (Week 12, 40)	Semi-Annual Visit (Week 26)	End of Study / Early Termination Visit  (Week 52)
Quality of Life Questionnaire (SF-36/ Child Health Questionnaire)		X					X	X
Serum Ferritin		X				X	X	X
Liver MRI/LIC	X 						X	X
Cardiac MRI T2*	X 						X	X
Dose Calculation/Verify and adjust dose level		X			X	X	X	
Contact IVRS/IWRS		X			X	X	X	X
Dispense study medication		X			X	X	X	
Dispense Patient Diary Card		X			X	X	X	
Review and Collect Diary Card					X	X	X	X
Medical events/Adverse events	X	X		X	X	X	X	X
Concomitant medications				X	X	X	X	X
Transfusion information (if applicable) 			X		X	X	X	X
Return used and unused study medication					X	X	X	X

X- To do, V- To verify, R- To review

1. Hematology testing is to be done weekly up to Week 26 and biweekly thereafter.
2. Early Termination: if patient withdraws from the study prior to Week 52, the patient must be seen for an early termination visit.
3. These evaluations must be done within 14 days prior to baseline visit. Females of childbearing potential must be making use of an approved birth control method at least one month prior to starting study medication.
4. Results from these tests will be considered the baseline values.
5. Height will only be measured at screening/baseline, semi-annual and Week 52 visits.
6. These evaluations must be conducted within two months prior to starting study medication
7. Collect volume of blood that the patient received during the transfusion and the mean hematocrit of the packed red blood cell units transfused.

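### Five visit sections of the protocol exempt emergency transfusions from recording, contradicting section 5.1 and the Schedule of Events, so a site following them would omit iron input

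*Protocol*

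**What the plan says.** Protocol section 5.1 sets two rules. The first concerns where transfusions happen: they are to be done at study visits, "except for those patients who may require emergency transfusion". The second concerns recording: "Data of all transfusions performed during the trial", with type, volume and mean hematocrit, "must be recorded in the eCRF and source documents". The emergency exception belongs to the first rule only.

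The visit sections attach the exception to the recording instruction. Section 5.4 covers a patient who "has received blood transfusions since the last visit (except for those patients who received an emergency transfusion), record the type of transfusion". The same parenthesis, "except for those patients who received an emergency transfusion", recurs in 5.6 (monthly), 5.7 (quarterly) and 5.8 (Week 26). Section 5.9 (Week 52 or early termination) opens its instruction with "If the patient has received blood transfusions since the last visit (except for those patients who received an emergency transfusion".

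Footnote 7 of the Schedule of Events (Appendix 18.1, repeated under SAP Table 1) says: "Collect volume of blood that the patient received during the transfusion and the mean hematocrit of the packed red blood cell units transfused". It makes no exception for emergencies.

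The recorded data are used in four places:

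- the iron-input covariate in the primary LIC model (protocol 11.4.1.3, SAP 7.1);
- the same covariate in the cardiac T2* and serum ferritin models (protocol 11.4.1.3, SAP 7.2);
- the between-arm comparison of iron input (SAP 9.3);
- the in-study check of mean daily input against 0.3 mg/kg/day in both arms (protocol 6.1).

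**The concern.** One rule says to record everything; five visit checklists say not to record these details for patients who had an emergency transfusion. No precedence rule is stated. A coordinator who works through the visit section would be following the protocol in leaving the transfusion out, and the iron would be in the patient but not in the dataset.

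The exemption is worded by patient, not by transfusion. Read broadly, it would also drop that patient's routine transfusions since the last visit.

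Protocol section 1.1 names acute events such as stroke, acute chest syndrome and splenic sequestration among the reasons for transfusion in sickle cell disease, so emergency transfusions are plausible in this population. An error here enters an adjustment variable of the primary analysis and a quantity checked during treatment.

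**Working it through.** **1. The passages side by side**

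| Place | Emergency exception applies to | Emergency transfusion recorded? |
|---|---|---|
| Protocol 5.1 | performance at a study visit | yes, mandatory |
| Schedule footnote 7 | nothing | yes |
| Protocol 5.4, 5.6, 5.7, 5.8, 5.9 | the recording instruction | no, read literally |

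All five visit sections that carry the instruction conflict with the other two sources.

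**2. The SAP's own example (SAP 9.3)**

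Inputs: 1 mg iron per mL packed cells, 65% hematocrit of transfused units, 54 kg, 3 × 30.5 = 91.5 days.

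Iron per transfusion = volume given × hematocrit − volume removed × its hematocrit.

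- Simple: 1200 × 0.65 = 780 mg
- Exchange: 1250 × 0.65 − 1016 × 0.80 = −0.3, shown as 0 mg
- Partial exchange: 2500 × 0.65 − 1000 × 0.80 = 825 mg
- Simple: 1000 × 0.65 = 650 mg

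Total 2255 mg; 2255 / 54 / 91.5 = 0.456, which reproduces the stated 0.46 mg/kg/day.

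Now treat the 1200 mL simple transfusion as an unrecorded emergency (an assumption): (2255 − 780) / 54 / 91.5 = 1475 / 54 / 91.5 = 0.299. The 0.3 line corresponds to 0.3 × 54 × 91.5 = 1482 mg, so this one omission takes the example from above the line to just below it. Omitting the exchange row instead changes nothing.

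**3. One omitted simple transfusion**

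The volumes are assumed; hematocrit and weight are those of the SAP example.

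| Volume | Iron | mg/kg | Over 91.5 days | Share of 0.3 | Over 364 days |
|---|---|---|---|---|---|
| 500 mL | 325 mg | 6.02 | 0.066 | 22% | 0.017 |
| 1000 mL | 650 mg | 12.04 | 0.13 | 44% | 0.033 |

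The 91.5-day column relates to a 3-month input. The 364-day column is closer to the covariate in the primary model, with a fixed full-year denominator. The formula is volume × 0.65 / 54 / days.

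**4. Direction of the error in the average**

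SAP 9.3 divides the summed input by the days in months for which transfusion data were obtained. If a month's only transfusion goes unrecorded, the month may leave the denominator as well.

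Illustration (assumed): 54 kg, eleven months at 650 mg each (7150 mg), and a twelfth month whose only transfusion is an emergency one.

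- Emergency 325 mg, recorded: (7150 + 325) / 54 / 366 = 0.378.
- Emergency 780 mg, recorded: (7150 + 780) / 54 / 366 = 0.401.
- Not recorded, month dropped: 7150 / 54 / 335.5 = 0.395.
- Not recorded, month kept: 7150 / 54 / 366 = 0.362.

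If the month is dropped, the average is too high in the first case (0.395 against 0.378) and too low in the second (0.395 against 0.401). If it is kept, the average is too low in both. The recorded total is too low whenever the omitted transfusion carried net iron.

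**The case against.** The strongest reply is that the matter is settled elsewhere. Section 5.1 is explicit and mandatory, section 8 sends sites to Appendix 18.1 for the measurements at each visit, and footnote 7 there has no exemption. The parenthesis looks like the visit-timing exception of 5.1 carried into the wrong sentence. That is a fair inference, and it makes this a drafting slip rather than a choice. A site following 5.1 or footnote 7 loses nothing. But five repetitions of the opposite instruction, with nothing saying which prevails, do not make recording reliable.

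A reader might infer more than the documents support:

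- **That omissions would be common.** Section 1.1 lists indications for prevention and treatment together and gives no rate of emergency transfusion. Section 6.2 describes the transfusion regimen of these patients as similar to that in thalassemia major. The frequency is unknown.
- **That the covariate would be understated.** This holds for the recorded total, but not necessarily for the SAP's study average.
- **That the primary comparison is biased.** The exemption reads the same in both arms, nothing shows differential omission, and no effect on the treatment difference or its confidence interval has been derived.
- **That the 0.3 mg/kg/day check would often change.** It requires input above the line for at least three consecutive months, and spreading one transfusion over 91.5 days is only one reading of that. Patients already in the upper dosing category from baseline are not moved by it.
- **That stratification is affected.** That factor uses transfusion history before baseline.

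**Conclusion.** The contradiction is real and stands in the current text of all five visit sections. Following the visit text would leave out data that the analysis needs. Recorded total and 3-month input would be too low by the net iron omitted; the study-average covariate could err either way.

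The size per omitted transfusion is an illustration. It rests on a simple transfusion, an assumed volume, and the hematocrit and weight of the SAP example; for an exchange it may be close to zero. The aggregate size cannot be stated, because neither the frequency of emergency transfusion nor the sites' actual practice is in the documents. This is a minor point, wrong as written, and worth correcting because the correction is cheap.

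**What to change.** Delete the parenthesis in protocol 5.4, 5.6, 5.7, 5.8 and 5.9, or reword it so that it covers only where and when an emergency transfusion is given. These sections then agree with 5.1 and footnote 7, and emergency transfusions are recorded with type, volume and hematocrit. Where the unit hematocrit is unavailable, use the site average that SAP 9.3 already uses.

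The edit still has a use: the SAP reports 17 patients on treatment and leaves the restart of enrolment to be decided after the interim analysis. For patients already treated, check adverse event and serious adverse event records and hospital source documents for unrecorded transfusions before database lock.

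The cost is a wording change and the retrieval of some records. No dosing rule is touched.
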